3.2.2.1.1. Adverse events of interest

The TEAEs of interest for additional reporting are: nausea, vomiting and diarrhoea (as defined based on preferred term). Based on emerging blinded data reviews, other AEs of interest may be added to this list, which would be documented with a SAP amendment or documented in the changes to planned analysis section in the CSR.

3.2.2.1.2. Subset Reporting Interval

A summary of adverse events occurring during a subset of the main reporting interval will be based on a shorter reporting window. This interval will include all TEAEs (reported separately) if:

• the event starts after or on the first dose, but doesn't start more than two days after the last dose of IP (defined as either completing the 26 weeks or 32 weeks (depending on cohort) of treatment or discontinuing from IP earlier).

3.2.2.2. Hypoglycemic Monitoring

Hypoglycemia AEs will be recorded in the AE Case Report Form (CRF) with details of the event captured on the Hypoglycemic Event Details CRF. Details of when these will be recorded are given in the protocol Section 8.2.5.

For programming purposes, the hypoglycemic AE categories are based on the following:

- Severe Hypoglycemia: Severe is checked in the severity criteria of the CRF. This assessment will be made by the PI based on the protocol definition.
- Documented Symptomatic Hypoglycemia: If (1 Did the participant have symptoms of hypoglycemia?) Yes and (2 – Was the blood glucose measured?) Yes and result <70 mg/dL on the CRF, but hypoglycemia is not classified as severe.
- Asymptomatic Hypoglycemia: If (1) No and (2) Yes and result <70 mg/dL on the CRF, but hypoglycemia is not classified as severe.
- Probable Symptomatic Hypoglycemia: If (1) Yes and (2) No and (2b If blood glucose was not measured, did symptoms resolve when treated with carbohydrate or glucagon?) Yes on the CRF, but hypoglycemia is not classified as severe.

3.2.2.3. Laboratory Data

Safety laboratory tests (hematology, chemistry, urine testing and other clinical laboratory tests) will be performed as described in the protocol.

To determine if there are any clinically significant laboratory abnormalities, the safety tests will be assessed against the criteria specified in the sponsor reporting standards. The assessment will take into account whether each participant's baseline test result is within or outside the laboratory reference range for the particular laboratory parameter.

Baseline for all laboratory measurements will be defined as the result closest prior to dosing at Visit 3 (Day 1).

PFIZER CONFIDENTIAL DMB02-GSOP-RF02 8.0 *Statistical Analysis Plan Template* TMF Doc ID: 98.03 Page 18 of 61

3.2.2.3.1. Change from Baseline Summaries

Focused change from baseline summaries (including both absolute changes from baseline and percent change from baseline, calculated separately) of the following safety laboratory endpoints will be assessed:

- Change from baseline in calcitonin to all post-dose time points as per the SOA
- Change from baseline in amylase to all post-dose time points as per the SOA
- Change from baseline in lipase to all post-dose time points as per the SOA
- Change from baseline in thyroid stimulating hormone (TSH) to all post-dose time points as per the SOA
- Change from baseline in free thyroxine (free T4) to all post-dose time points as per the SOA
- Change from baseline in lipid profile (total cholesterol, direct LDL cholesterol, HDL cholesterol and triglycerides) to all post-dose time points as per the SOA
- Change from baseline in liver function tests (alanine transaminase [ALT], aspartate aminotransferase [AST], alkaline phosphatase, total bilirubin, bile acids and gamma-glutamyl tranferase [GGT]) to all post-dose time points as per the SOA
- Change from baseline in estimated glomerular filtration rate (eGFR) to all post-dose time points as per the SOA

3.2.2.1. Vital Signs

Vital sign measurements (blood pressure and pulse rate) will be taken as detailed in the Schedule of Activities given in the protocol. The average of the triplicate measurements collected at each appropriate assessment time will be calculated for each vital sign parameter.

Baseline will be defined as the average of the triplicate measurements at the visit closest prior to dosing at Visit 3 (Day 1).

Changes from baseline for supine systolic and diastolic blood pressure and pulse rate will be calculated for each post baseline measurement.

3.2.2.2. Electrocardiogram (ECG)

Standard 12-lead ECG (including heart rate, QT, QTcF, PR and QRS interval) will be obtained at times detailed in the Schedule of Activities given in the protocol.

Baseline will be defined as the measurement at the visit closest prior to dosing at Visit 3 (Day 1).

Change from baseline for heart rate, QT, QTcF, PR and QRS interval will be calculated for each post baseline measurement.

PFIZER CONFIDENTIAL DMB02-GSOP-RF02 8.0 *Statistical Analysis Plan Template* TMF Doc ID: 98.03 Page 20 of 61

3.2.2.3. Assessment of Mental Health as determined by Columbia-Suicide Severity Rating Scale (C-SSRS) and Patient Health Questionnaire-9 (PHQ-9).

The C-SSRS is a validated tool to evaluate suicidal ideation and behaviour. Data relevant to the assessment of suicidality will be mapped to the Columbia-Classification Algorithm of Suicide Assessment (C-CASA) codes as given in Appendix 5.

For this endpoint the screening visit will be labelled as 'Lifetime' in tables and the recent history (i.e. past 12 months) will also be reported separately. Baseline is defined as the last pre-dose measurement.

The PHQ-9 is a 9 item self-report scale for the assessment of depressive symptoms. The PHQ-9 will be completed by participants and reviewed by site staff at the pre-defined time points outlined in the schedule of activities.

The PHQ-9 total score will be derived for each time point separately by summing the responses to the 9 questions.

3.3. Other Safety Endpoint(s)

Not applicable.

3.4. Other Endpoint(s) (or, Exploratory Endpoints)

- Trough plasma concentrations of danuglipron at time points specified in the SoA.
- CFB in fasting plasma insulin, homeostatic model assessment of insulin resistance (HOMA-IR) and homeostatic model assessment of beta-cell function (HOMA-B) at:
 - Weeks 4, 8, 12, 16, 22 and 26 for Cohorts 1 and 2.
 - Weeks 4, 8, 16, 20, 24, 28 and 32 for Cohort 3.

HOMA-IR is calculated as: (fasting plasma insulin [FPI] × fasting plasma glucose [FPG])/405

HOMA-B is calculated as: (360 × FPI) / (FPG - 63)

In both cases above, FPI concentration is in mIU/L and the FPG concentration is in mg/dL.

- Absolute CFB in waist circumference at:
 - Weeks 2, 4, 6, 8, 10, 12, 16, 18 and 22 for Cohorts 1 and 2.
 - Weeks 4, 8, 12, 16, 20, 24 and 28 for Cohort 3.

The average of the triplicate waist measurements collected at each assessment time will be calculated prior to summaries/analysis. If any of the triplicates are missing, the non-missing value(s) will be used, and missing values will not be imputed.

- Absolute CFB in waist-to-hip ratio at:
 - Weeks 2, 4, 6, 8, 10, 12, 16, 18 and 22 for Cohorts 1 and 2.

PFIZER CONFIDENTIAL DMB02-GSOP-RF02 8.0 *Statistical Analysis Plan Template* TMF Doc ID: 98.03 Page 21 of 61 • Weeks 4, 8, 12, 16, 20, 24 and 28 for Cohort 3.

The average of the triplicate waist and hip measurements collected at each assessment time will be calculated prior to calculating the waist-to-hip ratio at each assessment time. If any of the triplicates are missing, the non-missing value(s) will be used, and missing values will not be imputed.

• Shift from baseline in glycemic category (normoglycemia, pre-diabetes, or T2DM) at End of Treatment

For the purposes of reporting the shift in glycemic categories², the following definitions will be used:

Normoglycemia: FPG < 100 mg/dL and HbA1c < 5.7%; Pre-diabetes: FPG 100-125 mg/dL (both inclusive) or HbA1c 5.7-6.4% (both inclusive); T2DM: FPG \geq 126 mg/dL or HbA1c \geq 6.5%.

For discordant results between FPG and HbA1c with respect to the glycemic category criteria, the higher category will be used (eg, a participant with FPG of 124 mg/dL and HbA1c of 6.6% would be classified as T2DM).

- CFB in systolic and diastolic BP at each planned in-clinic study visit up through the End of Treatment visit.
- CFB in lipid parameters at:
 - Weeks 4, 8, 12, 16, 22 and 26 for Cohorts 1 and 2.
 - Weeks 4, 8, 12, 16, 20, 24, 28 and 32 for Cohort 3.
- CFB in SF-36v2® subscales and summary scores at:
 - \circ Weeks 16 and 26 at Weeks 16 and 26 for Cohorts 1 and 2.
 - Weeks 16, 24 and 32 for Cohort 3.

The SF-36v2®^{3,4} is a 36-item questionnaire that measures functional health and well-being from a patient's perspective. It is a generic questionnaire and can be used across age (adults), disease, and treatment groups. The questionnaire consists of 8 health domain scales: physical functioning (10 items), role-physical (4 items), bodily pain (2 items), general health (5 items), vitality (4 items), social functioning (2 items), role-emotional (3 items), mental health (5 items), reported health transition (1 item) and 2, physical and mental component summary scores. Each health domain scale raw score is transformed to 0-100 scale which can then be converted to norm-based T-scores (Mean=50, SD=10).

The following transformed norm-based T-scores will be derived: physical functioning (PF); role-physical (RP); bodily pain (BP); general health (GH); vitality (VT); social functioning (SF); role-emotional (RE); mental health (MH); reported health transition; physical component summary (PCS); and mental component summary scores (MCS).

PFIZER CONFIDENTIAL DMB02-GSOP-RF02 8.0 Statistical Analysis Plan Template TMF Doc ID: 98.03 Page 22 of 61

- CFB in Eating-Related Factors Daily Diary at:
 - Weeks 4, 8, 12, 16, 22 and 26 for Cohorts 1 and 2.
 - Weeks 4, 8, 12, 16, 20, 24, 28 and 32 for Cohort 3.

The Eating-Related Factors Daily Diary is a daily, self-administered questionnaire that measures eating-related factors. The diary consists of 5 items that ask participants to evaluate their hunger, appetite, fullness, and cravings in the past 24 hours.

At baseline and at the timepoints listed above, the 7-day average score will be calculated separately for each item. This average score will be based on the 7 days leading up to the respective week (i.e. for Week 4 it would be Day 22 up to Day 28) and will be considered missing when 4 or more days are missing in a 7 day period. Baseline is defined as the 7 days leading up to dosing on Day 1 (i.e. Day -7 up to and including Day -1). The change from baseline for each post-dose time point will then be calculated for each of the 5 items separately.

• CFB in PGI-S at each planned in-clinic study visit up through the End of Treatment visit.

The PGI-S is a supportive item recommended by FDA for use as an anchor measure to generate an appropriate threshold that represents meaningful within-patient change in the target patient population. There are 4 PGI-S items that ask participants to evaluate the severity of their hunger, appetite, fullness, and cravings in the past 7 days.

The PGI-S should be converted to a numeric scale using the following mapping:

Response	Numeric value
None	0
Mild	1
Moderate	2
Severe	3

The change from baseline to each post-dose time point will then be calculated.

- CFB in PROMIS® Fatigue at:
 - Weeks 16 and 26 for Cohorts 1 and 2.
 - Weeks 16, 24 and 32 for Cohort 3.

The PROMIS® Fatigue⁵ Custom 9-item Version is a self-reported measure that assesses a range of symptoms in the past 7 days from mild subjective feelings of tiredness to an overwhelming, debilitating, and sustained sense of exhaustion that likely decreases one's ability to execute daily activities and function normally in family or social roles. A global raw score ranging from 9 to 45 is calculated and can be translated into a T-score (Mean=50, SD=10) using the applicable score conversion table.

See Appendix 6 for derivation of the PROMIS Fatigue T-scores.

PFIZER CONFIDENTIAL DMB02-GSOP-RF02 8.0 *Statistical Analysis Plan Template* TMF Doc ID: 98.03 Page 23 of 61

- CFB in PROMIS® Physical Function at:
 - Weeks 16 and 26 for Cohorts 1 and 2.
 - Weeks 16, 24 and 32 for Cohort 3.

The PROMIS® Physical Function⁶ Custom 13-item Version is a self-reported measure that assesses capability rather than actual performance of physical activities. It includes assessment of one's ability to walk, climb stairs, run/jog, exercise as well as instrumental activities of daily living. A global raw score ranging from 13 to 65 is calculated and can be translated into a T-score (Mean=50, SD=10) using the applicable score conversion table.

See Appendix 7 for derivation of the PROMIS Physical Function T-scores.

- CFB in IWQOL-Lite-CT© at:
 - Weeks 16 and 26 for Cohorts 1 and 2.
 - Weeks 16, 24 and 32 for Cohort 3.

The IWQOL-Lite-CT©⁷ was developed for use in the context of clinical trials for obesity, with 20 items addressing concerns that are specifically relevant to the study population.

The responses to the 20 items will be summarised at each visit using the following 3 scores: physical composite score; physical function score; and psychosocial composite score. These are derived as outlined in Appendix 8. The change from baseline for each post-dose time point (as applicable) will then be calculated for each of the 3 scores.

- PGI-C at:
 - Weeks 4, 16 and 26 for Cohorts 1 and 2.
 - Weeks 4, 16, 24 and 32 for Cohort 3.

The PGI-C is a supportive item recommended by FDA for use as an anchor measure to generate an appropriate threshold that represents meaningful within-patient change in the target patient population. There are 4 PGI-C items that ask participants to rate the overall change in their hunger, appetite, fullness, and cravings since they started taking the study medication.

3.5. Baseline Variables

Baseline measures will be included as a covariate in all applicable statistical models along with the stratification variable of biological gender (female versus male) at screening.

The statistician may conduct further exploratory analyses into the effect of covariates and factors (such as age and strata) on the efficacy endpoints. If conducted, and considered relevant to the clinical study report (CSR), the methods will be fully justified and discussed within the report.

PFIZER CONFIDENTIAL DMB02-GSOP-RF02 8.0 *Statistical Analysis Plan Template* TMF Doc ID: 98.03 Page 24 of 61

4. ANALYSIS SETS (POPULATIONS FOR ANALYSIS)

Data for all participants will be assessed to determine if participants meet the criteria for inclusion in each analysis population prior to unblinding and releasing the database and classifications will be documented per standard operating procedures.

Participant Analysis Set	Description
Enrolled	"Enrolled" means a participant's agreement to participate in a clinical study following completion of the informed consent process. Potential participants who are screened for the purpose of determining eligibility for the study, but do participate in the study, are not considered enrolled, unless otherwise specified by the protocol.
Randomly assigned to study intervention	All participants randomly assigned to study intervention regardless of whether or not study intervention was administered.
Evaluable	All participants randomly assigned to study intervention and who take at least 1 dose of study intervention. Participants will be analyzed according to the randomized study intervention.
Safety	All participants randomly assigned to study intervention and who take at least 1 dose of study intervention. Participants will be analyzed according to the study intervention they actually received.

Defined Analysis Set	Description
Estimand Set 1	All participants randomly assigned to study intervention and who take at least 1 dose of study intervention.For participants who discontinue study intervention, all subsequent values will be censored.
Estimand Set 2	All participants randomly assigned to study intervention and who take at least 1 dose of study intervention and do not have major protocol deviations. Major protocol deviations will be reviewed prior to database lock to identify such participants (described in Section 4.1). For participants who discontinue study intervention, all subsequent values will be censored.
PK Concentration Set	All participants randomly assigned to study intervention and who take at least 1 dose of PF-06882961 (danuglipron) and in whom at least 1 concentration value is reported.

4.1. Identifying Major Protocol Deviations

Major protocol deviations will be identified by review of each protocol deviation on a caseby-case basis to determine whether the associated subject should be excluded from the Estimand Set 2. The list of potential deviations that could be classified as major are: falsely enrolled into study despite violating inclusion/exclusion criteria; non-compliance with study medication; and use of prohibited medications. Other deviations that are identified during the study based on emerging data that are deemed to qualify as major may also be considered. The project statistician will ensure that the list of subjects and the reason for exclusion is clearly documented and provided to programming prior to unblinding and releasing the database.

4.2. Strata Misallocations

Participants who are randomized to the wrong stratum (male/female), in error, will have the incorrect stratum assignment remain in IMPALA but the clinical database will include the correct stratum. The latter will subsequently be used for all relevant analyses.

5. GENERAL METHODOLOGY AND CONVENTIONS

5.1. Hypotheses and Decision Rules

The null hypothesis that there is no difference between danuglipron and placebo will be tested for the primary endpoint and efficacy related secondary and tertiary endpoints. The alternative hypothesis is that danuglipron is superior (i.e. greater reduction) to placebo on the primary endpoint.

Statistical inference will be based on the primary endpoint: percent change from baseline in body weight at End of Treatment.

The Type I error rate (α -level) used for the statistical inference will be 5% (1-sided).

Each treatment group of danuglipron will be tested separately compared to placebo. The slow titration arms will be considered separate treatment groups, to the standard titration arms.

No adjustment for multiple comparisons will be made.

For all other endpoints there will be no formal hypothesis testing.

5.2. General Methods

The analyses related to the primary, secondary and exploratory endpoints will be based on the appropriate population for analysis (see Section 4).

Unless otherwise stated, all summaries, analyses and plots will be presented by treatment group with separate tables for Cohorts 1 & 2 combined and Cohort 3. The following treatment group labels (or similar) will be used:

Cohorts 1 & 2

Placebo PF-06882961 40mg BID (1-week titration)

> PFIZER CONFIDENTIAL DMB02-GSOP-RF02 8.0 *Statistical Analysis Plan Template* TMF Doc ID: 98.03 Page 26 of 61

PF-06882961 80mg BID (1-week titration) PF-06882961 120mg BID (1-week titration) PF-06882961 160mg BID (1-week titration) PF-06882961 200mg BID (1-week titration) PF-06882961 120mg BID (2-week titration) PF-06882961 200mg BID (2-week titration)

Cohort 3

Placebo PF-06882961 80mg BID (4-week titration) PF-06882961 140mg BID (4-week titration) PF-06882961 200mg BID (4-week titration)

5.2.1. Analyses for Continuous Endpoints

Continuous variables will be presented using summary statistics: number of observations, arithmetic mean, standard deviation, median and range (minimum and maximum) values. For endpoints to be analysed on the natural log_e scale, the geometric mean and geometric coefficient of variation will additionally be calculated (excluding change from baseline summaries).

5.2.2. Analyses for Categorical Endpoints

Categorical variables will be presented using summary statistics: number of observations, counts and percentages.

5.2.3. Mixed Model Repeated Measures (MMRM)

The MMRM model(s) will include treatment, time, strata (females versus males) and treatment-by-time interaction as fixed effects, baseline as a covariate and the baseline-by-time interaction with time fitted as a repeated effect and participant as a random effect.

An unstructured covariance matrix will be used to estimate the variances and covariance within participant across time points. If convergence is not obtained or model fit is not adequate, then other covariance structures will be investigated as necessary. The Kenward-Roger approximation will be used for estimating degrees of freedom for the model parameters.

Missing values (e.g. due to censoring) will be implicitly imputed as part of the MMRM model fitting.

The Least Squares Means (LSMeans) together with 90% confidence intervals, standard errors and p-values (2-sided) will be obtained for each treatment group at each time point.

Differences in LSMeans between each treatment group of danuglipron relative to placebo at each time point, together with 90% confidence intervals, standard errors and p-values (2-sided), will also be obtained.

Example SAS code is provided in Appendix 3.

PFIZER CONFIDENTIAL DMB02-GSOP-RF02 8.0 Statistical Analysis Plan Template TMF Doc ID: 98.03 Page 27 of 61

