The primary analysis will include all participants randomly assigned to study intervention and who take at least 1 dose of randomized study intervention. The MMRM models will include treatment, time, strata (females versus males) and treatment-by-time interaction as fixed effects, baseline as a covariate and the baseline-by-time interaction with time fitted as a repeated effect and participant as a random effect. Baseline body weight will be included on the loge scale. An unstructured correlation matrix will be used, and the Kenward-Roger approximation will be used for estimating degrees of freedom for the model parameters. Missing values will be imputed as part of the MMRM model assumptions and no adjustments will be made for multiplicity. The modelled mean loge-differences and 90% CIs for the loge-differences at End of Treatment will be extracted from the model and exponentiated to provide estimates of the relative difference in each PF-06882961 treatment arm reported separately, compared to placebo.

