1.2. Schema

Figure 1. Overall Study Schema for Cohorts 1 and 2

[figure not shown]
[figure not shown]
[figure not shown]

Figure 2. Overall Study Schema for Cohort 3

[figure not shown]
[&]quot;T" denotes visit planned as a telephone contact

Figure 3. Titration Schema for Cohorts 1 and 2

^{*} Placebo (Arm 1) n=67 which includes Cohort 1 (n=60) and Cohort 2 (n=7). The 2-week titration arms (Arms 7, 8 and 9) n=34 per arm which includes Cohort 1 (n=20) and Cohort 2 (n=14).

Figure 4. Titration Schema for Cohort 3

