There will be total of approximately 581 participants across all 3 cohorts of this study. In Cohort 1, approximately 420 participants (approximately 60 in each of the placebo and 5 1-week titration PF-06882961 arms and approximately 20 in each of the 3 2-week titration PF-06882961 arms) were randomized. All dosing arms, including placebo, were enrolled simultaneously in Cohort 1. Subsequently, in Cohort 2, approximately 49 additional participants were randomized to the placebo and 2-week titration arms (approximately 7 in the placebo and approximately 14 in each of the 3 2-week titration arms.). Combining Cohorts 1 and 2, there were a total of approximately 469 participants randomized (approximately 67 in the placebo, approximately 60 in each of the 5 1-week titration arms and approximately 34 in each of the 3 2-week titration arms). In Cohort 3, approximately 112 participants will be randomized to 4 additional study arms (approximately 16 in the placebo and approximately 32 in each of 3 PF-06882961 arms with 4-week titration steps).

Randomization is stratified according to biological gender (female versus male), as both tolerability and efficacy may be different between men and women. This stratification is intended to balance the numbers of participants of either gender across treatment arms. In addition, no more than approximately 70% of the trial population will consist of 1 gender, in order to permit adequate representation of both men and women in the trial population.

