6.3. Measures to Minimize Bias: Randomization and Blinding

6.3.1. Allocation to Study Intervention

[figure not shown]
Assignment of placebo in the run-in period and allocation of participants to treatment groups for the double-blind treatment period will proceed through the use of an IRT system (IWR). The site personnel (study coordinator or specified designee) will be required to enter or select information including but not limited to the user's ID and password, the protocol number, and the participant number. For the placebo run-in, the site personnel will then be provided with a DU or container number; for the double-blind treatment period, the site personnel will then be provided with a randomization number, and DU or container number(s). The IRT system will provide a confirmation report containing the participant number, randomization number, and DU or container number(s) assigned. The confirmation report must be stored in the site's files.

For Cohort 1, a randomization code using the method of random permuted blocks will be utilized to randomize eligible participants in 3:3:3:3:3:1:1:1 (placebo: 5 1-week titration PF-06882961 arms: 3 2-week titration PF-06882961 arms) prior to the first dose of double-blinded study intervention. For the additional participants enrolled as part of Cohort 2, a randomization code using the method of random permuted blocks will be utilized to randomize eligible participants in 1:2:2:2 (placebo: 3 2-week titration PF-06882961 arms) prior to the first dose of double-blinded study intervention. For Cohort 3, a randomization code using the method of random permuted blocks will be utilized to randomize eligible participants in 1:2:2:2 (placebo: 3 4-week titration PF-06882961 arms) prior to the first dose of double blinded study intervention. Participants will be randomized to 1 of the blinded study intervention regimens described in Table 3 for Cohorts 1 and 2, and Table 4 for Cohort 3.

Table 3. Target Doses for Randomized Regimens for Cohorts 1 and 2

| Regimen Description (dosed twice daily) | Cohort 1 | Cohort 2 | CCI | Total Number of Tablets per dose |
|---|----------|----------|-----|--|
| Placebo | х | Х | CCI | |
| PF-06882961 – 40 mg (1-week titration steps) | Х | | | |
| PF-06882961 – 80 mg (1-week titration steps) | X | | | |
| PF-06882961 – 120 mg (1-week titration steps) | X | | | |
| PF-06882961 – 160 mg (1-week titration steps) | X | | | |
| PF-06882961 – 200 mg (1-week titration steps) | X | | | |

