9.4.1.1. Analyses for Continuous Endpoints

The MMRM model(s) will include treatment, time, strata (females versus males) and treatment-by-time interaction as fixed effects, baseline as a covariate and the baseline-by-time interaction with time fitted as a repeated effect and participant as a random effect. An unstructured correlation matrix will be used, and the Kenward-Roger approximation will be used for estimating degrees of freedom for the model parameters.

Missing values will be imputed as part of the MMRM model assumptions.

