6. ANALYSES AND SUMMARIES

Data collected before baseline will only be listed, unless otherwise stated.

For all endpoints, baseline is defined in Section 3.

For Cohorts 1 and 2, End of Treatment is defined as Week 26. For Cohort 3, End of Treatment is defined as Week 32.

Data from participants enrolled into the original cohort (Cohort 1) and Cohort 2 will be combined for reporting, where data from the placebo and 2-week titration arms will be combined from the 2 cohorts and analyzed together. Data from participants enrolled into Cohort 3 will be analyzed and reported separately unless otherwise specified.

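### Cohorts 1 and 2 were randomised separately at different placebo to 2-week ratios but are pooled with no cohort term, so any cohort shift d biases each 2-week versus placebo contrast by 0.307 × d

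*SAP*

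**What the plan says.** Protocol 4.1 describes sequential enrolment: "Subsequently, in Cohort 2, approximately 49 additional participants were randomized to the placebo and 2-week titration arms". Protocol 6.3.1 gives the second cohort its own code: "For the additional participants enrolled as part of Cohort 2, a randomization code using the method of random permuted blocks will be utilized", at 1:2:2:2. The footnote in Protocol 1.2 gives the make-up of the pooled arms. For placebo it reads "Placebo (Arm 1) n=67 which includes Cohort 1 (n=60) and Cohort 2 (n=7". For the 2-week arms it reads "n=34 per arm which includes Cohort 1 (n=20) and Cohort 2 (n=14". The five 1-week arms exist in Cohort 1 only.

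SAP section 6 then pools: "data from the placebo and 2-week titration arms will be combined from the 2 cohorts and analyzed together". The primary model in SAP 5.2.3 is specified as "The MMRM model(s) will include treatment, time, strata (females versus males) and treatment-by-time interaction as fixed effects, baseline as a covariate", plus baseline-by-time. Protocol 1.1 ("The MMRM models will include treatment, time, strata (females versus males) and treatment-by-time interaction as fixed effects, baseline as a covariate") and 9.4.1.1 ("The MMRM model(s) will include treatment, time, strata (females versus males) and treatment-by-time interaction as fixed effects") agree. The logistic model (SAP 5.2.4), the imputation model (SAP 5.3.1) and the example code for both in Appendix 3 contain treatment, sex stratum and baseline, but not cohort.

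SAP 6.1.1.2 lists no cohort-adjusted analysis. SAP 3.5 and Protocol 9.1 leave room for optional covariate work and supporting estimands, but neither names cohort or commits to anything.

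**The concern.** Randomisation balances the arms within each cohort. When two cohorts have different allocation ratios, the pooled arms contain different mixes of them, and a simple pooled comparison is protected only if the cohorts have the same expected outcome. Cohort 2 came later, so its season, sites or participants could differ in ways that sex and baseline weight do not capture.

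Three contrasts are most exposed: 2-week versus placebo at each dose, each tested at one-sided 5% (SAP 5.1). The five 1-week contrasts are affected less and in the opposite direction, because their placebo group includes Cohort 2 participants and they do not. Both Emax models (SAP 5.2.5 and 5.2.6) have the same feature: placebo from both cohorts is set against active doses from Cohort 1 only. SAP 5.2.6 fits a separate MMRM to each arm with its own list of terms, so a change to 5.2.3 alone would not reach it.

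**Working it through.** **The plan's own counts.** Inputs are the arm sizes in Protocol 4.1 and 1.2. (The Cohort 1 ratio is printed with eight terms for nine arms, so the counts are used here.)
- Cohort 1: 6 × 60 + 3 × 20 = 420. Cohort 2: 7 + 3 × 14 = 49. Total 469, as stated.
- Pooled placebo 60 + 7 = 67; each 2-week arm 20 + 14 = 34, as stated.
- At 25% dropout: 67 × 0.75 = 50.25 and 34 × 0.75 = 25.5, matching the stated 50 and 25 completers in Protocol 9.2.

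The stated 80% power cannot be checked in absolute units because the difference and SD are redacted.

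**Bias factor.** Let d be the extra weight loss in Cohort 2, in percentage points, common to all arms and not explained by sex or baseline. Without a cohort term, the bias is d times the difference in Cohort 2 share.
- 2-week versus placebo: 14/34 − 7/67 = 0.4118 − 0.1045 = 0.307.
- 1-week versus placebo: 0 − 7/67 = −0.104.

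Least squares on the nine-arm design gives the same values. A check with ten visits, sex, baseline-by-time, 25% random dropout and between-visit correlation of 0.8 to 0.95 gives 0.301 to 0.314 and −0.101 to −0.105.

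**Standard error (SE).** Assumptions: SD 0.068 on the log scale, taken from the example code in SAP Appendix 2, treated as 6.8 points; 25% dropout in every cell.
- 2-week versus placebo: 6.8 × √(1/50.25 + 1/25.5) = 6.8 × √0.05912 = 1.65 points.
- 1-week versus placebo: 6.8 × √(1/50.25 + 1/45) = 6.8 × √0.04212 = 1.40 points.

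**Error and power.** One-sided error = 1 − Φ(1.645 ∓ bias/SE). Power in the adverse direction = Φ(2.4865 − 1.645 − bias/SE), where 2.4865 is the standardised effect that gives 80%.

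| 2-week versus placebo | 1-point shift | 2-point shift |
|---|---|---|
| Bias (points) | 0.31 | 0.61 |
| Error if Cohort 2 loses more | 7.2% | 10.1% |
| Error if Cohort 2 loses less | 3.4% | 2.2% |
| Power if Cohort 2 loses less | 74% | 68% |

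Over an assumed SD range of 0.05 to 0.09, a 1-point shift gives 8.2% to 6.6%, or 2.9% to 3.7% in the other direction. For 1-week versus placebo, the error at 1 point is 4.3% if Cohort 2 loses more and 5.8% if it loses less.

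**Across tests.** The eight tests are unadjusted by design. In simulation the chance of at least one false positive is about 24% with d = 0, 26% if Cohort 2 loses 1 point more and 23% if it loses 1 point less. For the three 2-week tests alone it is 12.9%, 17.9% and 8.9%.

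**With an additive cohort term.** Bias from a common shift becomes zero.
- 2-week versus placebo: variance factor 0.05912 to 0.06318, SE 1.65 to 1.71 (ratio 1.034), power Φ(2.4865/1.034 − 1.645) = 77.6%.
- 1-week versus placebo: 0.04212 to 0.04259 (ratio 1.006), power 79.6%.
- The unadjusted 2-week estimate has the smaller mean squared error when |d| is below 6.8 × √(0.06318 − 0.05912)/0.3073 = 1.41 points (1.04 at SD 0.05, 1.87 at SD 0.09).

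**The case against.** The best counter-argument has four parts.

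- **d may well be zero.** The chance of placebo was the same in both cohorts (60/420 = 7/49 = 1/7), so expectation of active drug was the same. Tablet count, packaging, run-in and schedule of activities were also shared. No mechanism for d is documented. This makes a large shift less likely, but an equal overall placebo share does not equalise the cohort mix between placebo and any one active arm, so the 0.307 factor stands.
- **Adjustment has a certain cost against an uncertain gain.** At a 1-point shift the mean squared error is 1.653² + 0.307² = 2.83 unadjusted and 1.709² = 2.92 adjusted. This is correct, and it is the strongest reason for the sponsor to prefer a sensitivity analysis. But a smaller mean squared error does not keep the stated 5% error rate.
- **This is a phase 2b study with unadjusted tests.** The effect on the chance of any false positive is indeed small, 24% to 26%. Each contrast is nonetheless declared as a one-sided 5% test.
- **Optional analyses are already allowed.** They are, but a check chosen after unblinding is weaker than a pre-specified one.

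**Conclusion.** The gap is real and should be closed. The counts, the pooling and the missing cohort term are in the documents, and the factors 0.307 and −0.104 follow from planned counts alone, given equal dropout across arms and cohorts. The size of any bias is conditional: d is unknown, the SD of 0.068 comes from example code, and the 1- and 2-point shifts are illustrations. On those assumptions a 1-point shift moves the 2-week error from 5% to 7.2% or 3.4%. The conclusion is that the plan relies on d = 0 without a planned check, not that the trial is biased. Adjustment removes only a shift common to all arms; one that differs by arm would remain in part.

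**What to change.** For the combined Cohorts 1 and 2 analyses only:

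1. **Main model (SAP 5.2.3; Protocol 9.4.1.1 and 1.1).** Add: *Cohort (1 versus 2) and cohort-by-time will be included as fixed effects. LSMeans will be evaluated at the observed cohort proportions, with the weighting of sex unchanged.* Say which set defines those proportions. On planned counts 49/469 = 7/67, so the placebo LSMean does not move with d; equal weights would move it and every other LSMean by (0.5 − 0.104) × d = 0.396 × d. The 1-week LSMeans will be extrapolated to a 10.4% Cohort 2 mix, a shift of 0.104 × d that cancels in the contrasts.
2. **Responder analysis (SAP 5.2.4 and 5.3.1; Protocol 9.4.1.2).** Add cohort to the logistic and imputation models. In Appendix 3, add it to the PROC TRANSPOSE BY, PROC MI CLASS and VAR, and PROC LOGISTIC CLASS and MODEL statements. The odds ratio then becomes conditional on cohort as well.
3. **Second Emax model (SAP 5.2.6).** Fit the placebo MMRM on Cohort 1 placebo only, or include cohort and evaluate that LSMean at Cohort 1. Reconcile the description of placebo in Appendix 2, and note that the two Emax models will then report placebo at different cohort mixes.

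If the sponsor keeps its primary model, commit in SAP 6.1.1.2 to the cohort-adjusted MMRM as a named sensitivity analysis. A Cohort 1-only analysis is a weaker substitute: its 2-week SE is 6.8 × √(1/15 + 1/45) = 2.03 points, 23% larger.

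**Cost.** No new data are needed. The SE rises 3.4% for 2-week versus placebo, which costs the same power as an adverse shift of about 0.44 points, and 0.6% for 1-week. In SAP 5.2.6, Cohort 1 placebo alone raises the placebo SE by 5.7% (√(67/60)) and the dose versus placebo SE by 2.7%. SAP 5.2.3 also governs the secondary, HOMA, laboratory, vital-sign and ECG MMRMs, so their combined-cohort versions gain the terms too. Changing the primary model may need a protocol amendment (Protocol section 9). The sensitivity analysis leaves the primary model and its power unchanged.
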